Informed consent will be sought for completion of the study eligibility screening and for participation in the study via oral and written consent respectively. Some patients may be incapable of providing informed consent. In such cases, informed consent will be obtained from their surrogate decision-maker. Surrogate decision-makers will be identified as the individual who is making decisions on behalf of the patient for clinical care in the ICU. Consent will be obtained in two steps. First, oral consent will be obtained to perform a brief (< 5 minute) in-bed assessment of muscle strength using a standardized protocol to determine eligibility. Only those patients who are weak, defined either by (a) composite muscle strength sum-score, using Medical Research Council (MRC) scale, <48/60, or (b) a handgrip strength of <11 kg in men and <7 kg in women(2), will be offered written informed consent (since demonstrated muscle weakness is an entry criteria). During the written informed consent process details on the intent of the proposed study, its design, the type of information collected, and potential risks and benefits of participation will be discussed. If surrogates were consented because of the patient's incapability, we will monitor the patient for return of capability and once they are capable, acquire consent from them for continuation in the study.

4-a-2) Planned flow of participants through the study

After consent is obtained, a chart review will be performed to ensure patient still meets eligibility and safety criteria (sections 5 and 4-f, respectively).

4-a-3) Randomization

After informed consent is obtained, eligible patients will be randomly assigned in a 2:1 ratio to the intervention (lorcaserin) or control group (placebo) respectively. (Please see Table 3 and section 4-a-6 for detailed study events.) Group assignment will be masked for patients, clinical and research staff administering the lorcaserin/placebo, and assessing outcomes (muscle strength, safety outcomes, or serum sample collection), as discussed under section 4-c.

4-a-4) Measurement of Exposures and Potential Confounders:

Patient exposures and potential confounders will be collected at study enrollment and are outlined in Table 1. Table 2 summarizes ICU-related exposures and possible confounders that will be collected during the study.

Table 1: Patient-related exposures and potential confounders – Baseline status

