Patient Risk Factors	Method for data collection	Measurement Scale
Age/sex/race/ethnicity	Chart review	Continuous/Binary/Categorical
Weight/Height	Chart review	Continuous
Comorbidities: Charlson* & Functional Indices**	Chart review	Ordinal
Severity of illness: APACHE II***	Chart review	Continuous
Leg/Hand dominance	Patient/Proxy interview	Binary
Past Psychiatric History***	Chart review	Categorical

*Charlson Comorbidity index: a score derived from 19 categories of comorbidities, with an increased score reflecting an increased likelihood of one-year mortality(20).

**Functional Comorbidity Index: An 18 item list of diagnoses which uses physical function as the outcome of interest, with increased score indicative of decreased function(21).

Date: 1 August 2016

Principal Investigator: [name] PhD

Application Number: IRB00072940

****Acute Physiology and Chronic Health Evaluation (APACHE II): An index of disease severity that takes into account age, pre-existing medical conditions, and 12 acute physiologic variables that are assessed during the first 24 hours of ICU admission. Scored on a scale from 0-71, with higher scores indicating more severe disease and increased mortality risk(22).*

Table 2: Potential confounders – ICU status

ICU exposure risk factors	Method of Data Collection	Measurement Scale
Sequential Organ Failure Assessment (SOFA) Score**	Chart review	Continuous
ICU admission diagnosis details	Chart review	Categorical

** *SOFA: A composite score that takes into account 6 organ systems used to assess the severity of organ dysfunction in ICU(23), collected on Days 1 and 3.*

4-a-5) Sequence and Timing of Study Events

On Day 1, intervention and control group participants receive 10 mg of lorcaserin or placebo, respectively. Both groups also will undergo assessments before and after administration of lorcaserin/placebo (for assessment details and times, see table 3 and section 4-a-6)

On Day 2, the intervention and control group participants will not receive any lorcaserin/placebo, but will undergo repeat assessments (for assessment details and times, see table 3 and section 4-a-6)

On Day 3, the intervention and control group participants receive 30 mg of lorcaserin or placebo, respectively. Both groups also will undergo assessments before and after administration of lorcaserin/placebo (identical to Day 1).

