On Day 4, the intervention and control group participants will not receive any lorcaserin/placebo, but will undergo assessments (identical to Day 2).

4-a-6) Measurements

Participants will be monitored to ensure safety of lorcaserin/placebo administration. This monitoring will include a daily review of interim history (via chart review), medications, and laboratory values (details below), as well as assessment for changes in mental status and monitoring for serotonin syndrome (see table 3).

We also will obtain a battery of outcome measures to test the efficacy in improving muscle strength and assess the safety of lorcaserin, as described in tables 3.

All monitoring will be done by assessors blinded to group allocation.

Table 3: Safety and Efficacy Measures (numbers indicate the number of times within each study day that each measurement is performed)

Measurement	Number of assessments			
	Day 1*	Day 2†	Day 3***‡	Day 4†
Safety Measures				
Chart Review	1	1	1	1
Laboratory Tests (details below)	1	1	1	1
EKG	2	1	1	1
RASS sedation score	2***	1	2***	1
CAM-ICU delirium screen	2***	1	2***	1
Neuro Psychiatric Screen	2	1	1	1
Hunter Serotonin Toxicity Criteria	1	1	1	1

Efficacy Measures				
Handgrip Strength (Primary Outcome)	2***	1	2***	1
Arm & leg strength (MMT using MRC Scale)	2***	1	2***	1
Quadriceps Strength using handheld dynamometry	2***	1	2***	1
Lorcaserin serum drug levels [‡]	1	1	1	1
Electromyography & Nerve Conduction Study	once only to assess for any peripheral neuromyopathy****			

MMT: Manual muscle strength testing; MRC: Medical Research Council; HHD: Hand-Held Dynamometry; EKG: Electrocardiogram; RASS: Richmond Agitation Sedation Scale; NPI-C: Neuropsychiatric Inventory - Clinician Rating Scale; CAM-ICU: Confusion Assessment Method for the ICU; Hunter Criteria: will be used to evaluate patients for serotonin syndrome (24)

* 10 mg of lorcaserin or placebo administered

** 30 mg of lorcaserin or placebo administered

*** measures are performed as close to the time as drug or placebo administration as possible (within 4 hours) and as soon as possible (between 2 - 6 hours) after drug or placebo administration, on Days 1 and 3 only

**** EMG & NCS will be performed at any time point after the patient is randomized into study, and will be used to help interpret the results of strength tests

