‡ Peak concentration serum samples will be collected 2 hours ± 15 minutes or 3 hours ± 15 minutes after drug administration (see section 4-a-6.11 for details) and trough concentration serum samples will be collected 24 hour ± 30 minutes after drug administration (see section 4-a-6.11 for details)

† Days 2 and 4 are consecutive to days 1 and 3 respectively.

‡ Day 3 may or may not be consecutive to day 2 depending on assessor availability.

Safety Measures

4-a-6.1) *Chart Review*: A daily review of participants' medical records for interim medical history and medications will be performed to monitor for any safety issues and ensure that participants continue to meet eligibility and safety criteria (see sections 5 and 4-f respectively).

4-a-6.2) *Laboratory Tests*: As indicated in table 3 above, participants will undergo daily blood draws for the following standard laboratory tests: Heme 8 and CMP. In particular, laboratory tests will be obtained prior to every dose of lorcaserin or placebo to ensure that patients meet eligibility and safety criteria (see sections 5 and 4-f respectively). If the relevant tests have already been done for clinical purposes, they will NOT be repeated for research purposes. As these labs are typically measured, at least daily, in the ICU setting, they may not need to be drawn for research purposes and the pre-existing values will be reviewed for research purposes.

4-a-6.3) *EKG*: Daily EKGs will be obtained to determine if participants develop bradycardia, new-onset QT prolongation (as defined in Section 4.f.3.4 below) or new 2nd or 3rd degree AV block. In particular, this test will be obtained prior to every dose of lorcaserin or placebo to ensure that patients meet eligibility and safety criteria (see sections 5 and 4-f respectively). If this test has already been done for clinical purposes, it will NOT be repeated for research purposes. As this test is commonly done, at least daily, in the ICU setting, it may not need to be done for research purposes and the pre-existing test will be reviewed for research purposes.

Date: 1 August 2016

Principal Investigator: [name] PhD

Application Number: IRB00072940

4-a-6.4) Richmond Agitation Sedation Scale (RASS)(25): is a validated instrument to measure agitation and sedation status in ICU patients. Participants will be screened for their sedation status daily as well as pre- and post-drug or placebo administration as indicated in table 3 above.

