 - ii. If the dosage of any interacting agent (e.g., analgesic) is routinely titrated for desired clinical effect, the clinical team will be informed and cautioned to ensure titration occurs with the consideration for potentiation or decrease in the interacting agent's effect.
 - iii. If neither substitution, temporary discontinuation or titration of a potential interacting agent is possible, the patient will be excluded / withdrawn from the study.

4-e) Justification for inclusion of a placebo or non-treatment group.

In our proposed study, patients will be randomized to receive either lorcaserin or Placebo. The FDA-approved drug under study in this trial, lorcaserin, does not have any published data supporting efficacy for muscle weakness in the ICU. Hence, no therapy known to be effective is being withheld from the placebo group. Given that our primary and secondary outcomes are based on semi-objective assessments of muscle strength or subjective assessments of cognitive/psychological symptoms, a control group (with blinded outcomes assessments) is required to reduce bias in patients' outcome assessment. Patients in the control group will continue with routine therapy as deemed appropriate by the clinical team.

4-f) Definition of treatment failure or participant removal criteria.

1. Participants will be removed from this study if the surrogate decision-maker, the patient (when capable of medical decision-making) or the patients' medical team makes a request for removal from the study.
2. As stated in Section 4-d, in the event a participant is scheduled to receive pharmacologic therapies that may potentially interact with the study drug (see appendix A), and substitution, gradual titration or discontinuation of interacting agent is not safe or feasible, within the decision rules outlined in Section 4-d, the participant will be withdrawn from the study.
3. The study drug or placebo will be discontinued for the following physiologic changes. Data collection will continue in these participants.
 1. An increase AST > 8 times the upper limit of normal (ULN)
 2. An increase in ALT > 8 times ULN,
 3. A decrease in creatinine clearance <30 mL/min,
 4. New-onset Q-T prolongation, defined as
 - QTc>500 msec
 - A >60 msec increase in QTc from baseline
 5. New-onset 2nd or 3rd degree heart block without a permanent pacemaker,
 6. Persistent heart rate <60 bpm
 7. New-onset priapism
 8. Serotonin Toxicity (as determined by Hunter Criteria, as previously described)

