 9. New-onset psychosis
 10. Onset of new symptoms of hallucinations or euphoria (as determined by NPI-C assessment as described above)
4. If the patient is given a sedative medication during this brief period between baseline and follow-up testing, with a change in mental status that prohibits the ability to perform muscle strength testing, no further testing or administration of lorcaserin/placebo will be done in that patient and a new patient would be recruited and consented in place of this patient.

4-g) Description of what happens to participants receiving therapy when study ends or if a participant's participation in the study ends prematurely.

Those who end their participation in this study prematurely will not be given any further lorcaserin/placebo doses. Similarly, lorcaserin/Placebo administration will cease upon the end of the study. Cessation of lorcaserin will not be harmful to the patient. There are no known adverse effects associated with withdrawal of lorcaserin and there is no need for tapering. Thus its absence or cessation will not directly cause any adverse outcomes. Patient care will continue without change after cessation of lorcaserin/placebo.

5) Inclusion/Exclusion Criteria

5-a) Inclusion Criteria:

1. Age \geq 18 years old
2. Sepsis [\geq 2 Systemic Inflammatory Response Syndrome (SIRS) Criteria AND known or suspected infection]
3. Muscle weakness [Medical Research Council sum score $<$ 48/60 or handgrip strength $<$ 11 kg in men and $<$ 7 kg in women]
4. Obey Commands [Score for DeJonghe Awakening Score of \geq 3/5]

5-b) Exclusion Criteria (based on medical record review and discussion with patient/surrogate)

1. Severe renal insufficiency [Creatinine Clearance $<$ 30 mL/min – or receiving dialysis]
2. Acute infectious or auto-immune hepatitis, acute liver failure, or a history of cirrhosis without liver transplant
3. History of psychosis
4. Bradycardia, or 2nd or 3rd degree AV block without pacemaker
5. History of valvular heart disease without valve replacement
6. History of priapism
7. Receiving drugs with serotonergic effects and/or CYP2D6 substrates which cannot be substituted stopped or titrated (as described in section 4d).
8. Receiving Sulfonylurea medication at the time of the study
9. Prior neuromuscular or central nervous system disease, including pre-existing neuropathy
10. Inability to perform study's muscle strength assessments based on patient's baseline status prior to hospital admission

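### Section 4-f item 4 ends testing in, and replaces, an already randomised patient whom a sedative has made untestable, with no by-arm accounting and no stated precedence over item 3

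*Combined protocol and SAP*

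**What the plan says.** - Section 4-a-3: once consent is given, "eligible patients will be randomly assigned in a 2:1 ratio". Strength testing around each dose comes after this.
- Section 4-f item 4: the trigger is a sedative given between the baseline and follow-up tests, with a mental-status change that rules out strength testing. The consequence is "no further testing or administration of lorcaserin/placebo will be done in that patient and a new patient would be recruited and consented in place".
- Section 4-f item 3: study drug stops after listed changes, which include serotonin toxicity, new psychosis, hallucinations and euphoria. It then adds: "Data collection will continue in these participants". It does not say which data.
- Section 4-f items 1 and 2 separately cover removal on request and withdrawal because of interacting drugs.
- Section 7-a compares the change in grip at 30 mg with control by t-test. Section 7-b(1) repeats this at 10 mg, 7-b(3) pairs the two doses, and 7-b(4) is a PK-PD model that pools all subjects and time points over the four days. Section 7-c sets 10 lorcaserin and 5 placebo patients.
- Section 7 names no analysis set and does not mention replaced patients. The nearest record-keeping text is the reason for an untested muscle group (4-a-6.10) and the count of unblinding episodes (4-c). Neither is a by-arm account of replacements.

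**The concern.** Replacement after randomisation is a problem when treatment could affect the event that triggers it. Section 8-a lists euphoria and dissociation at supratherapeutic lorcaserin doses, and item 3 itself anticipates psychiatric events and serotonin toxicity. A sedative given in response would bring item 4 into play. Under section 8-c, agitation and delirium are not reportable unless judged related to the protocol, so the event behind the sedation need not appear as a reported adverse event either.

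Three things are at stake: safety follow-up in a dosed patient, if *testing* means all assessments; later strength observations that the PK-PD analysis would use; and a visible record of who was randomised, to which arm, and why they left.

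**Working it through.** **1. The plan's own figure.** With SD 9 kg and r = 0.8, the SD of change is 9 × √(2 × (1 − 0.8)) = 5.69 kg. For 10 and 5 patients, two-sided 0.05 (sidedness assumed) and 80% power, the detectable difference is (1.960 + 0.842) × 5.69 × √(1/10 + 1/5) = 8.73 kg by normal approximation, or 9.45 kg by noncentral t. The stated 9 kg is consistent with this. The point does not rest on a sample-size error.

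**2. Assessments scheduled in Table 3.**

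| | Day 1 | Day 2 | Day 3 | Day 4 |
|---|---|---|---|---|
| Strength (grip, MMT, quadriceps) | 6 | 3 | 6 | 3 |
| Safety (seven measures) | 11 | 7 | 9 | 7 |

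Strength totals 6 + 3 + 6 + 3 = 18 per patient.

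**3. Strength tests stopped (either reading).** The same-day post-dose set of 3 is lost to sedation in any event and is not counted.
- Day 3 case: in hand 6 + 3 + 3 = 12; stopped by item 4 = 3 (Day 4).
- Day 1 case: in hand 3; stopped by item 4 = 3 + 3 + 3 = 9 (Days 2 to 4). Because item 4 also ends dosing, Day 3 has one set, not a pre/post pair.

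**4. Safety assessments stopped (literal reading only).**
- Day 3 case, Day 3 dose given: post-dose RASS and CAM-ICU, 2, plus Day 4, 7, = 9. Day 3 items whose timing relative to the dose is not given could add to this.
- Day 1 case, Day 1 dose given: 2 + (3 × 7) = 23, or 25 if the second Day 1 EKG and neuropsychiatric screen follow the dose.

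Table 3 and section 4-a-5 do not agree on the Day 3 EKG and neuropsychiatric screen. That mismatch exists without item 4 and belongs in a separate comment; the counts here follow Table 3.

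**5. Items 3 and 4 side by side.** Suppose a patient hallucinates after a dose and is given a sedative. Item 3 keeps data collection going and item 4 ends testing.
- If data collection includes strength tests, the items conflict on later strength tests under either meaning of *testing*.
- If data collection means safety data only and *testing* means strength testing only, they do not conflict.
- If data collection means safety data and *testing* means every assessment, they conflict on safety.

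The text settles neither term and gives no order of precedence.

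**6. Values already obtained.** Section 7-b(4) includes them by its own wording. The t-tests are silent. A Day 3 case has a completed Day 1 pair, which 7-b(1) could use. Sections 7-a and 7-b(3) need the missing Day 3 post-drug value.

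**7. Accounting (counts assumed).** One replacement leaves 1/16 = 6% of randomised patients outside the 15; two leave 2/17 = 12%. If the new patient were freshly randomised 2:1, the chance of landing in the same arm would be 2/3 for a lost lorcaserin patient and 1/3 for a lost placebo patient, so the 10 and 5 split is not guaranteed.

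**The case against.** This is a 15-patient convenience pilot with a narrow trigger: a sedative in a short window, followed by loss of testability. Overlap with item 3 is narrower still. Item 4's sentence is about strength testing, so reading it to end safety checks is strained, and section 8-c still requires serious unanticipated or study-related adverse events to be recorded and reported. Replacement also protects the planned numbers: with 9 and 5 patients the t-based detectable difference would rise from 9.45 to 9.69 kg.

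The PK-PD loss is also smaller than the counts suggest. With the 11-hour half-life in 4-a-6.11, the fraction of a Day 1 dose remaining is 0.5^(24/11) = 22% at 24 hours, 0.5^(48/11) = 5% at 48 hours and 0.5^(72/11) = 1% at 72 hours. Of the 9 tests in a Day 1 case, the 6 on Days 3 and 4 add little to the concentration range.

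Most of this stands and limits the weight of the point. It does not supply a by-arm count, an allocation rule or a precedence between items 3 and 4. Sedation may also have worn off by the next study day, when item 4 still bars testing.

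Three stronger inferences are tempting and should not be drawn. A reader might infer that replacement shifts the lorcaserin mean by some number of kilograms. The documents do not support this: the 30 mg comparison needs the same-day post-drug grip value, which an untestable patient lacks whether replaced or not, so any such shift comes from untestability and would survive the fix. A reader might infer that items 3 and 4 flatly contradict each other; step 5 shows that this depends on an undefined term. A reader might infer that replaced patients' data are discarded or left out of safety counts; no section says so.

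**Conclusion.** The point holds as a minor to moderate defect in the rule and its reporting. Item 4 ends testing in a patient who is already randomised and possibly dosed, and replaces that patient without by-arm accounting or a stated allocation for the newcomer.

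Under the natural reading it stops 3 later strength assessments in a Day 3 case, and 9 in a Day 1 case with no further dose. Under the literal reading it also ends 9 safety assessments by Table 3 in a Day 3 case. Items 3 and 4 may conflict where both apply. The t-tests do not say whether values in hand are used, whereas 7-b(4) already pools them.

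The safety counts assume that the dose on the day of sedation was given. How often item 4 will apply cannot be derived from the documents, and no bias in the primary comparison is attributed to replacement.

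**What to change.** Leave the dosing instruction in item 4 unchanged, and reconcile items 3 and 4:
- State that ending further testing does not stop the scheduled safety assessments in a dosed patient, unless that patient is removed under item 1 or withdrawn under item 2.
- State which item governs later strength tests when both apply.
- Keep every dosed patient in the safety denominator and every randomised patient in a by-arm accounting.
- Use strength values already obtained, such as a completed Day 1 pair in 7-b(1).
- Treat the new patient as an addition, and state how that patient is allocated.
- Report item 4 cases by arm and by timing relative to dose.

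**Cost.** If only strength testing was meant to stop, the safety part is wording alone. If all testing was meant, the cost is the 9 safety assessments of a Day 3 case or the 23 to 25 of a Day 1 case, all already scheduled. Of the 21 on Days 2 to 4, 9 (chart review, laboratory tests, EKG) may be covered by routine care, leaving 12 bedside screens; for the EKG, "If this test has already been done for clinical purposes, it will NOT be repeated for research purposes". A Day 1 case may need more than four calendar days of follow-up, since "Day 3 may or may not be consecutive to day 2 depending on assessor availability". Some grip values will be openly reported as missing. No enrolment is needed beyond the replacement already planned.
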